1. PURPOSE OF STUDY

This study represents the third phase of a larger research project developed for a U01 award as part of the Collaborative Initiative on Fetal Alcohol Spectrum Disorders (CIFASD) funded by the National Institute on Alcohol Abuse and Alcoholism (NIAAA). The overall project aims to develop and evaluate a mobile health (mHealth) application (app) for parents/caregivers of children with fetal alcohol spectrum disorders (FASD). The primary focus of the FMF Connect app is to provide parent/caregiver education and support.

The first phase of this project was approved under IRB protocol #1266 (legacy RSRB#67394). In that phase we used qualitative research methods to engage parents and caregivers in the development of the mHealth intervention and obtain iterative feedback on acceptability and feasibility. A prototype of the app was developed in both iOS and Android and beta-testing was completed with parents/caregivers and providers. In the second phase of the study, we conducted a feasibility trial of the FMF Connect app with parents/caregivers under IRB protocol #4433. This included quantitative pre-post surveys and qualitative interviews with a subsample of users to optimize the intervention and trial procedures. In this third phase, we will conduct a larger scale randomized controlled trial (RCT) to test the efficacy of the FMF Connect app for parents/caregivers of children with FASD. We hypothesize that participants who receive the FMF Connect app (with or without the additional Coaching Module) will have improve outcomes relative to the waitlist control group. We anticipate the Coaching Module will increase participant engagement and usage of the FMF Connect app. Finally, we hypothesize that parental attributions of behavior targeted by the FMF Connect app will mediate intervention effects on child behavior and parenting self-efficacy.

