4. STUDY DESIGN

This study involves a three arm RCT with equal allocation to the following conditions: (1) FMF Connect + coaching, (2) FMF Connect alone, and (3) waitlist control. Quantitative survey data will be collected at three timepoints: baseline (T1), 6-weeks (T2), and 12-weeks (T3). The T2 timepoint will involve an abbreviated battery designed to allow statistical tests of mediation hypotheses (see Data Analysis Plan below). Primary study outcomes include child behavior, parent FASD knowledge,

parenting self-efficacy, behavior attributions, family needs met, and parent use of self-care. We are also interested in participant ratings of app quality and patterns of app usage. App usage will be recorded through AWS during the study period. After T3, study participants in the waitlist control group will receive the FMF Connect app.

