9. STUDY PROCEDURES

Data Collection & Randomization Procedures

Parents/caregivers who are eligible for the study will be sent an email inviting them to complete the baseline study surveys (see survey battery below) administered by REDCap. Participants will be

asked to enter their zip code to verify their identity when completing baseline and follow-up surveys (this will be verified against value entered in demographic surveys in the screening module). Families deemed ineligible after detailed review will be informed of their status.

Following baseline survey completion, participants will be randomized to one of three arms of the RCT:

1. FMF Connect app + text based coaching (within the app)
2. FMF Connect app (without coaching)
3. Waitlist control

Randomization will occur through the REDCap Randomization module, with an equal allocation pattern across groups. Participants will be notified of their group status via email. Emails for parents/caregivers in either of the FMF Connect app intervention groups (groups 1 and 2) will also include instructions of how to install the FMF Connect app on their devices. The email for the parents/caregivers in the FMF Connect app + coaching group (group 1) will inform them that they will receive an introductory email from their assigned coach in the next few days. Details about the FMF Connect app and Coaching interventions and described below.

All participants regardless of group assignment will receive emails through REDCap at 6 weeks and 12 weeks inviting them to complete follow-up surveys, along with a personalized link (see survey battery below). The assessment battery is estimated to take 35-45 minutes to complete at T1 and T3; T2 is estimated at 15-20 min. Waitlist control participants will receive the FMF Connect app following T3 survey completion.

Measure	Baseline (T1)	6-Weeks (T2)	12-Weeks (T3)
Eyberg Child Behavior Inventory (5-8min)	X		X
Reasons for Children’s Behavior Scale (4-6min)	X	X	X
Everyday Life Scale (4-6min)	X	X	X
Parenting Sense of Competence Scale (3-5min)	X	X	X
Family Needs Questionnaire (3-5min)	X		X
Knowledge & Advocacy Questionnaire (15-20min)	X		X
Self-Care and Support Assessment (3-5min)	X		X
Adverse Childhood Experiences (2 min)	X		
Family Background & Services Survey (5-10min)	X		X
COVID-19 Experiences Survey (5 min)			X
User Version of the Mobile Health Application Rating Scale (5-8min)			X

FMF Connect mHealth Intervention

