19. DATA ANALYSIS PLAN

Aim 1: For the two intervention groups, compare patterns of app usage (i.e., frequency, duration, use of core components) that relate to greater improvements in child and caregiver outcomes. Assess whether FMF Connect + Coaching results in higher usage of the app relative to FMF Connect alone.

A series of Multiple Regression analyses will test how app usage (i.e., frequency, duration, content/components accessed) relates to change in outcomes (i.e., parenting efficacy, FASD knowledge, family needs, child behavior) over time, controlling for pre-intervention level of functioning. With a sample size of 100 (n=50 per intervention group) and assuming $\alpha = .05$, there will be power .80 to detect small/medium effects ($f^2=.10$), .94 to detect medium effects ($f^2=.15$), and power $> .99$ to detect large effects ($f^2=.35$).

Aim 2: Examine whether families randomized to the three study arms differ in outcomes.

Repeated Measures Analysis of Variance will test whether families randomized to FMF Connect groups demonstrate improved outcomes relative to the waitlist group at 12 weeks. Pairwise comparisons will test for differences among intervention groups to determine if coaching adds additional benefit. Assuming a correlation among repeated measures ranging from .3 to .5 ($\alpha = .05$), with a sample of 150 and 3 time points, there will be power between .87-.96 to detect a small/medium effect ($f=.175$) and $>.99$ to detect medium and large effects ($f=.25$ and $f=.40$).

Aim 3: Examine whether parental attributions of child misbehavior mediate intervention-related changes in parenting efficacy and child behavior.

Mediation analyses will test whether parental attribution mediates the effects of FMF Connect on parenting efficacy and child behavior, including baseline levels of the respective outcomes. Given a sample size of 150, there will be adequate power ($>.80$) to detect small/medium effects within the mediation models using the bias-corrected bootstrap method.

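### Aim 3 does not say that baseline attributions enter the mediation models, so the attribution-to-outcome path may be confounded by attributions held before the trial

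*Combined protocol and SAP*

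**What the plan says.** Section 1 makes mediation a trial hypothesis: "we hypothesize that parental attributions of behavior targeted by the FMF Connect app will mediate intervention effects on child behavior and parenting self-efficacy". Section 4 explains the 6-week survey by this purpose: "The T2 timepoint will involve an abbreviated battery designed to allow statistical tests of mediation hypotheses".

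The analysis itself is in section 19, Aim 3, which tests whether parental attribution "mediates the effects of FMF Connect on parenting efficacy and child behavior, including baseline levels of the respective outcomes". That is the only covariate rule given for the mediation models. Aim 1 also adjusts for baseline, but only in the app-usage regressions. Section 4 does list attributions among the primary outcomes: "parenting self-efficacy, behavior attributions, family needs met, and parent use of self-care".

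The measure schedule in section 9 includes the "Reasons for Children’s Behavior Scale (4-6min") at T1, T2 and T3. It is taken here as the attribution measure, although the documents do not say so. The T1 survey precedes allocation: "Following baseline survey completion, participants will be randomized to one of three arms of the RCT". All three scales given at T2 are also given at T1, so a pre-randomisation value exists whichever of them is the mediator.

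**The concern.** A mediation claim multiplies two paths: arm to attributions, and attributions to outcome. Randomisation protects the first. It does not protect the second, because caregivers are not randomised to their T2 attributions. Attributions held at T1 can drive both T2 attributions and the T3 outcome. Adjusting for the T1 outcome removes only the part of that confounding that runs through the T1 outcome.

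If T1 attributions are absent from the outcome equation and the app shifts attributions at all, a pre-existing association can appear as a significant indirect effect. The trial would then report a mechanism that it has not shown.

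**Working it through.** **The plan's own figure.** Aim 3 states power above .80 at N = 150 for small/medium effects but gives no path values, so it cannot be reproduced directly. With two equal standardised paths and a bias-corrected bootstrap, power is .55 at .20, .83–.84 at .26 and .94 at .30. The statement is attainable for paths of about .26 or more, and it does not bear on this point.

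**Candidate models.** X is arm, M attributions, Y outcome; the digits are time points. The T2-mediator, T3-outcome order is inferred, because the Eyberg Child Behavior Inventory is not given at T2.

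- Natural reading: M2 on X; Y3 on X, M2, Y1.
- Own-baseline reading: M2 on X, M1; Y3 on X, M2, Y1.
- Full adjustment: M2 on X, M1; Y3 on X, M2, M1, Y1.

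**Inputs.** From the documents: N = 150; equal allocation; the bias-corrected bootstrap; and pooling of the two app arms to 100:50, following the section 1 hypothesis about "participants who receive the FMF Connect app (with or without the additional Coaching Module"). The shift in attributions borrows Aim 2's f = .175: .175/√(2/3 × 1/3) = .175/.471 = 0.37 SD. A larger shift of 0.57 SD is assumed as well.

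Assumed, not in the documents: true attribution-to-outcome path zero; T1 attribution-outcome correlation r = .4; outcome carry-over .5; attribution stability ρ = .5 (the top of Aim 2's range, "Assuming a correlation among repeated measures ranging from .3 to .5"); and slope g of Y3 on M1, given Y1 and M2, from 0 to .3.

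**Bias in the path when M1 is left out of the outcome equation.**

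bias = g·ρ·(1 − r²)/(1 − ρ²r²) = g × .5 × .84/.96 = .4375g

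For g = .1/.2/.3 this is .044/.088/.131. Simulation gave about .045/.085/.13, and zero with M1 included. The spurious indirect effect at a 0.37 SD shift is .4375g × 0.37 = .016/.032/.049. For comparison, a true path of .27 gives .27 × 0.37 = .10.

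**False-mediation rate.** 2,000 simulated trials per cell, 1,000 bootstrap draws each; Monte Carlo standard error about 0.5 point near 5% and 1.1 points near 40%.

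| Slope g | Natural, 0.37 SD | Own-baseline, 0.37 SD | Natural, 0.57 SD |
|---|---|---|---|
| 0 | 4.6% | – | 8.5% |
| .1 | 9.9% | – | 13.3% |
| .2 | 21.4% | 24.7% | 30.6% |
| .3 | 37.5% | 43.4% | 55.8% |

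Full adjustment gives 5.8%–6.5% at 0.37 SD and stability .5. Over all 24 cells (stability .3/.5/.7, slopes 0–.3, both shifts) it gives 5.7%–9.0%; the excess over 5% belongs to the bias-corrected interval itself. The own-baseline column shows that the outcome equation is the one that matters.

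**How far the rates move with the assumptions.**

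- Stability .3, slopes .2/.3, 0.37 SD: 10.5%/18.0% on the natural reading.
- App does not move attributions: 0.3%–6.8% over stability .3–.7 and slopes 0 and .3.
- Outcome residual variance fixed at .75, slopes .2/.3, 0.37 SD: 17.9%/30.3%.
- All scores at reliability .8, slope .3: 27.2% falls to 7.2% with full adjustment (0.37 SD), and 43.2% to 9.0% (0.57 SD).
- One stable trait drives both measures (cross-correlation .2/.3): 24.1%/42.7% falls only to 14.7%/26.0% (0.37 SD), and 34.9%/62.7% to 18.4%/34.5% (0.57 SD).

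**The case against.** The strongest case is that this is under-specification rather than a stated error. The plan prints no equations, and the natural reading is an inference. Because section 4 counts attributions as a primary outcome, the covariate phrase could be read to include them; if every baseline enters every equation, the problem is already solved. That reading is possible, but the Aim 3 sentence itself names only parenting efficacy and child behavior. If each equation takes only its own baseline, the result is the own-baseline column above, which is no better. The text has to say which applies.

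The second objection is that the larger rates come from demanding scenarios. With unit variances and no true path, the correlation of T1 attributions with the T3 outcome is g + .5 × .4, that is .2/.3/.4/.5 at slopes 0/.1/.2/.3. At slope .2 the association does not decay over 12 weeks from its concurrent value of .4, and at .3 it grows. This is a fair criticism. Slopes 0 to .1 are less strained; there the natural reading gives 4.6%–9.9% and the spurious indirect effect is at most .016.

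It is also fair that the covariate is only a partial remedy under a shared trait, that it can cost power when attributions are very stable, and that a mechanism analysis carries less weight than the efficacy comparison. These points limit the size of the concern. They do not supply a reason to leave T1 attributions out of the outcome equation.

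**Conclusion.** The concern holds as a conditional one. The plan does not state that T1 attributions enter the outcome equation, and two of the three readings leave the unrandomised path open to confounding. The harm ranges from none (slope 0, or an app that does not move attributions) through about double the nominal rate at slope .1 to 21%–56% at slopes .2–.3 with stability .5. All of these rest on assumed stability, correlation and slope, and none is a forecast. Aim 2 is not touched. This should be corrected before analysis, because a stated hypothesis depends on it; it does not threaten the trial as a whole.

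**What to change.** Print both equations in Aim 3: T2 attributions on arm and T1 attributions; T3 outcome on arm, T2 attributions, T1 attributions and T1 outcome. Name the scale that measures attributions. State that any mediation claim assumes no remaining mediator-outcome confounding, since the adjustment is incomplete under measurement error or a shared stable trait. A sensitivity analysis giving the residual mediator-outcome correlation at which the indirect effect would be zero is recommended but not essential.

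No new data are needed: the cost is one covariate already collected before randomisation. The effect on power depends on attribution stability, which the documents do not give. At a true path of .27, slope 0 and outcome residual variance .75:

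| Stability | 0.37 SD, natural → full | 0.57 SD, natural → full |
|---|---|---|
| .3 | .63 → .65 | .90 → .91 |
| .5 | .61 → .69 | .91 → .91 |
| .7 | .61 → .73 | .89 → .79 |
| .8 | .61 → .65 | .89 → .66 |

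Within Aim 2's .3–.5 range, power is unchanged or higher. The loss appears only at higher stability combined with the larger shift; it should be acknowledged beside the Aim 3 power statement, with the stability assumed.
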